10.1.7.1. Data Handling and Record Keeping

It is the investigator's responsibility to maintain essential study documents (records and documents pertaining to the conduct of this study and the distribution of IMP, including regulatory documents, eCRFs, signed participant ICFs, laboratory test results, IMP inventory records, source documents, relevant correspondence, AE reports, and all other supporting documentation) as required by the applicable national regulatory requirements. The study site should plan on retaining such documents for approximately 25 years after study completion. The study site should retain such documents until at least 2 years after the last approval of a marketing application in an ICH region and until there are no pending or contemplated marketing applications in an ICH region, or at least 2 years after the formal discontinuation of clinical development of the IMP. The sponsor will notify the principal investigator of these events.

These documents should be retained for a longer period if required by the applicable regulatory requirements or the hospital, institution, or private practice in which the study is being conducted. Participant identification codes (participant names and corresponding study numbers) will be retained for this same period of time. These documents may be transferred to another responsible party, acceptable to the sponsor, who agrees to abide by the retention policies. The investigator is required to notify the sponsor (or an authorized representative) in writing prior to changing the location or status of any essential clinical study documents. The investigator must contact the sponsor prior to disposing of any study records.

No records may be destroyed during the retention period without the written approval of the sponsor. No records may be transferred to another location or party without written notification to the sponsor.

For studies conducted outside the US under an US investigational new drug (IND), the principal investigator must comply with US Food and Drug Administration IND regulations and with those of the relevant national and local health authorities.

10.1.7.2. Quality Assurance Audit

Study processes, study sites (including, but not limited to site visits, central laboratories, vendors), the study database, and study documentation may be subject to quality assurance audit during the course of the study by the sponsor or sponsor's designee (CRO or other vendor) on behalf of sponsor. In addition, inspections may be conducted by regulatory bodies at their discretion. Such audits/inspections can occur at any time during or after completion of the study.

10.1.7.3. Quality Control

Quality control will be applied to each stage of study-related activities.

Clinical Study Protocol ARGX-113-2001 v2.0 Efgartigimod IV and SC

The following steps will be taken to ensure the accuracy, consistency, completeness, and reliability of the data:

- Investigator meetings
- Central laboratories for clinical laboratory parameters
- Site initiation visit
- Routine site monitoring
- Ongoing site communication and training
- Ongoing oversight by sponsor's designated CRO monitors of safety parameters and adherence to selection criteria
- Data management quality control checks
- Continuous data acquisition and cleaning
- Quality control check of the clinical study report (CTR)
- To avoid interobserver variability, every effort should be made to ensure that the same individual who made the initial baseline determinations completes all efficacy and safety evaluations

In addition, periodic audits can be performed as specified in Section 10.1.7.2.

When audits or inspections are conducted, access must be authorized for all study-related documents including medical history and concomitant medication documentation to authorized sponsor's representatives and regulatory authorities.

10.1.8. Source Documents

- Source documents provide evidence for the existence of the participant and substantiate the integrity of the data collected. Source documents are filed at the investigator's site.
- Data entered in the eCRF that are transcribed from source documents must be consistent with the source documents or the discrepancies must be explained. The investigator may need to request previous medical records or transfer records, depending on the study. Also, current medical records must be available.
- Definition of what constitutes source data can be found in the data management plan.
- The investigator must maintain accurate documentation (source data) that supports the information entered in the eCRF.
- Study monitors will perform ongoing source data verification to confirm that data entered into the eCRF by authorized site personnel are accurate, complete, and verifiable from source documents; that the safety and rights of participants are being protected; and that the study is being conducted in accordance with the currently approved protocol and any other study agreements, ICH GCP, and all applicable regulatory requirements.

10.1.9. Study and Site Start and Closure

First Act of Recruitment

The study start date is the date on which the clinical study will be open for recruitment of participants.

The first act of recruitment is the first site open and will be the study start date.

Study/Site Termination

The sponsor or designee reserves the right to close the study site or terminate the study at any time for any reason at the sole discretion of the sponsor. Study sites will be closed upon study completion. A study site is considered closed when all required documents and study supplies have been collected and a study-site closure visit has been performed.

The investigator may initiate study-site closure at any time, provided there is reasonable cause and sufficient notice is given in advance of the intended termination.

Reasons for the early closure of a study site by the sponsor or investigator may include but are not limited to:

For study termination:

• Discontinuation of further study intervention development

For site termination:

- Failure of the investigator to comply with the protocol, the requirements of the IRB/IEC or local health authorities, the sponsor's procedures, or GCP guidelines
- Inadequate or no recruitment (evaluated after a reasonable amount of time) of participants by the investigator
- Total number of participants included earlier than expected

If the study is prematurely terminated or suspended, the sponsor shall promptly inform the investigators, the IECs/IRBs, the regulatory authorities, and any CROs used in the study of the reason for termination or suspension, as specified by the applicable regulatory requirements. The investigator shall promptly inform the participant and should assure appropriate participant therapy and/or follow-up

10.1.10. Publication Policy

- All information regarding ARGX-113 supplied by the sponsor to the investigator and all data generated as a result of this study are considered confidential and remain the sole property of the sponsor. The results of the study will be reported in a clinical study report (CSR). The CSR will be written in accordance with the ICH E3 guideline and will be submitted in accordance with local regulations.
- Any manuscript, abstract, other publication, presentation of the results, or information arising in connection with the study must be prepared with the sponsor and must be submitted to the sponsor for review and comment prior to submission for publication

or presentation. Study participant identifiers will not be used in the publication of results.

- The sponsor will comply with the requirements for publication of study results. In accordance with standard editorial and ethical practice, the sponsor will generally support publication of multicenter studies only in their entirety and not as individual site data. In this case, a coordinating investigator will be designated by mutual agreement.
- Authorship will be determined by mutual agreement and in line with International Committee of Medical Journal Editors authorship requirements.

10.2. Appendix 2: Clinical Laboratory Tests

- The tests detailed in Table 3 will be performed by the central laboratory.
- Protocol-specific requirements for inclusion or exclusion of participants are detailed in Section 5 of the protocol.
- Additional tests may be performed at any time during the study as determined necessary by the investigator or required by local regulations.
- Investigators must document their review of each laboratory safety report.

Laboratory Assessment	Parameters		
Hematology	Platelet count Red blood cell (RBC) count Hemoglobin Hematocrit	RBC Indices: Mean corpuscular volume (MCV) %Reticulocytes	White blood cell count with differential (% and absolute numbers) Neutrophils Lymphocytes Monocytes Eosinophils Basophils
Clinical chemistry	 Blood urea nitrogen (BUN) Creatinine Glucose (fasting for 8 hours) Calcium Glycosylated hemoglobin (HbA1c) Potassium Sodium Alkaline phosphatase (ALP)^a Lactate dehydrogenase (LDH) 	C-reactive protein (CRP) Aspartate aminotransferase (AST) Alanine aminotransferase (ALT) γ Glutamyl transferase (GGT) Bilirubin, total and direct Albumin	Cholesterol: Total LDL HDL Triglycerides International Normalized Ratio (INR) Activated Partial Thromboplastin Time (aPTT)
Routine urinalysis Screening tests	 (LDH) Specific gravity pH, glucose, protein, blood, ketones, bilirubin, nitrite, leukocyte esterase by dipstick Highly sensitive urine human chorionic gonadotropin (hCG) pregnancy test (for female participants of childbearing potential) Microscopic evaluation Virology: HIV 1&2 screen/p24 antigen, hepatitis B core, hepatitis B surface, and hepatitis be surface antigen; and hepatitis C antibody, SARS-CoV-2 testing Highly sensitive serum hCG pregnancy test (for female participants of childbearing potential) Total immunoglobulin (IgG) levels AChR-Ab serology 		
	AChR-Ab serology	none (FSH) (for female par	ticipants)

Table 3:	Protocol-Required Laboratory Tests
----------	------------------------------------

^a If alkaline phosphatase is elevated, consider fractioning.

10.3. Appendix 3: Total Blood Volume Collected From Each Participant

The maximum amount of blood collected from each participant is 350 mL. Repeat or unscheduled samples may be taken for safety reasons or technical issues with samples.

10.4. Appendix 4: AEs and SAEs: Definitions and Procedures for Recording, Evaluating, Follow-up, and Reporting

10.4.1. Definition of AE

AE Definition

- An AE is any untoward medical occurrence in a clinical study participant, temporally associated with the use of study intervention, whether or not considered related to the study intervention.
- NOTE: An AE can therefore be any unfavorable and unintended sign (including an abnormal laboratory finding), symptom, or disease (new or exacerbated) temporally associated with the use of study intervention.

Events to Be Collected as AEs

- Any abnormal laboratory test results (hematology, clinical chemistry, or urinalysis) or other safety assessments (eg, ECG, radiological scans, vital signs measurements), including those that worsen from baseline, considered clinically significant in the medical and scientific judgment of the investigator (ie, not related to progression of underlying disease).
- Exacerbation of a chronic or intermittent pre-existing condition including either an increase in frequency and/or intensity of the condition.
- New conditions detected or diagnosed after study intervention administration even though it may have been present before the start of the study.
- Signs, symptoms, or the clinical sequelae of a suspected intervention- intervention interaction.
- Signs, symptoms, or the clinical sequelae of a suspected overdose of either study intervention or a concomitant medication. Overdose per se will not be reported as an AE/SAE unless it is an intentional overdose taken with possible suicidal/self-harming intent. Such overdoses should be reported regardless of sequelae.
- "Lack of efficacy" or failure of expected pharmacological action" per se will not be reported as an AE or SAE. Such instances will be captured in the efficacy assessments. However, the signs, symptoms, and/or clinical sequelae resulting from lack of efficacy will be reported as AE or SAE if they fulfill the definition of an AE or SAE.

Events NOT to Be Collected as AEs

- Any clinically significant abnormal laboratory findings or other abnormal safety assessments which are associated with the underlying disease, unless judged by the investigator to be more severe than expected for the participant's condition.
- The disease/disorder being studied or expected progression, signs, or symptoms of the disease/disorder being studied, unless more severe than expected for the participant's condition.
- Medical or surgical procedure (eg, endoscopy, appendectomy): the condition that leads to the procedure is the AE.
- Situations in which an untoward medical occurrence did not occur (social and/or convenience admission to a hospital).
- Anticipated day-to-day fluctuations of pre-existing disease(s) or condition(s) present or detected at the start of the study that do not worsen.

10.4.2. Definition of SAE

An SAE Is Defined as Any Untoward Medical Occurrence That, at Any Dose:

Results in death

Is life-threatening

The term "life-threatening" in the definition of "serious" refers to an event in which the participant was at risk of death at the time of the event. It does not refer to an event, which hypothetically might have caused death, if it were more severe.

Requires inpatient hospitalization or prolongation of existing hospitalization

- In general, hospitalization signifies that the participant has been admitted (usually involving at least an overnight stay) at the hospital or emergency ward for observation and/or treatment that would not have been appropriate in the physician's office or outpatient setting. Complications that occur during hospitalization are AEs. If a complication prolongs hospitalization or fulfills any other seriousness criteria, the event will be considered as serious. When in doubt as to whether "hospitalization" occurred or was necessary, the AE should be considered serious.
- Hospitalization for elective treatment of a pre-existing condition that did not worsen from baseline is not collected as an AE.

Results in persistent or significant disability/incapacity

- The term disability means a substantial disruption of a person's ability to conduct normal life functions.
- This definition is not intended to include experiences of relatively minor medical significance such as uncomplicated headache, nausea, vomiting, diarrhea, influenza, and accidental trauma (eg, sprained ankle) which may interfere with or prevent everyday life functions but do not constitute a substantial disruption.

Is a congenital anomaly/birth defect

Other situations:

- Medical or scientific judgment should be exercised by the investigator in deciding whether SAE reporting is appropriate in other situations such as significant medical events that may jeopardize the participant or may require medical or surgical intervention to prevent 1 of the other outcomes listed in the above definition. These events should usually be considered serious.
- Examples of such events include invasive or malignant cancers, intensive treatment for allergic bronchospasm, blood dyscrasias, convulsions or development of intervention dependency or intervention abuse.

10.4.3. Recording and Follow-up of AEs and/or SAEs

AE and SAE Recording

- When an AE/SAE occurs, it is the responsibility of the investigator to review all documentation (eg, hospital progress notes, laboratory reports, and diagnostics reports) related to the event.
- The investigator will then record all relevant AE/SAE information.
- It is **not** acceptable for the investigator to send photocopies of the participant's medical records in lieu of completion of the AE form.

- There may be instances when copies of medical records for certain cases are requested. In this case, all participant identifiers, with the exception of the participant number, will be redacted on the copies of the medical records before submission.
- The investigator will attempt to establish a diagnosis of the event based on signs, symptoms, and/or other clinical information. Whenever possible, the diagnosis (not the individual signs/symptoms) will be documented as the AE/SAE.

Assessment of Severity

The investigator will make an assessment of intensity for each AE and SAE reported during the study. All AEs observed will be graded using the National Cancer Institute (NCI) Common Terminology Criteria for Adverse Events (CTCAE) version 5.0.

The grade refers to the severity of the AE. If a particular AE's severity is not specifically graded by the guidance document, the investigator is to use the general NCI CTCAE definitions of grade 1 through grade 5 following his/her best medical judgment, using the following general guideline:

- Grade 1: Mild; asymptomatic or mild symptoms, clinical or diagnostic observations only; intervention not indicated
- Grade 2: Moderate; minimal, local, or noninvasive intervention indicated; limiting ageappropriate instrumental activities of daily living (ADL) (eg, preparing meals, shopping for groceries or clothes, using the telephone)
- Grade 3: Severe; or medically significant but not immediately life-threatening; hospitalization or prolongation of hospitalization indicated; disabling; limiting self-care ADL (ie, bathing, dressing and undressing, feeding self, using the toilet, taking medications, and not bedridden)
- Grade 4: Life-threatening consequences or urgent intervention indicated
- Grade 5: Death related to an AE

NOTE: An AE that is assessed as severe should not be confused with an SAE. Severe is a category utilized for rating the intensity of an event, and both AEs and SAEs can be assessed as severe.

An event is defined as "serious" when it meets at least 1 of the predefined outcomes as described in the definition of an SAE, not when it is rated as severe.

Assessment of Causality

- The investigator is obligated to assess the relationship between study intervention and each occurrence of each AE/SAE as "related" or "not related."
- The investigator will use clinical judgment to determine whether there is a reasonable possibility that the IMP caused the AE.
- A "reasonable possibility" of a relationship conveys that there are facts, evidence, and/or arguments to suggest a causal relationship, rather than a relationship cannot be ruled out.
- Alternative causes, such as underlying disease(s), concomitant therapy, and other risk factors, as well as the temporal relationship of the event to study intervention administration will be considered and investigated.
- **Related** means that the AE cannot be explained by the participant's medical condition, other therapies, or an accident. The temporal relationship between the AE and IMP

administration is compelling and/or follows a known or suspected response pattern concerning that IMP.

- Not related means that the AE can be readily explained by other factors such as the participant's underlying medical condition, concomitant therapy, or accident. No plausible temporal or biologic relationship exists between the IMP and the AE.
- The investigator will also consult the Investigator's Brochure (IB) and/or Product Information, for marketed products, in his/her assessment.
- For each AE/SAE, the investigator **must** document in the medical notes that he/she has reviewed the AE/SAE and has provided an assessment of causality.
- There may be situations in which an SAE has occurred and the investigator has minimal information to include in the initial report to the sponsor. However, it is very important that the investigator always make an assessment of causality for every event before the initial transmission of the SAE data to the sponsor
- The investigator may change his/her opinion of causality in light of follow-up information and send an SAE follow-up report with the updated causality assessment.
- The causality assessment is 1 of the criteria used when determining regulatory reporting requirements.

Follow-up of AEs and SAEs

- The investigator is obligated to perform or arrange for the conduct of supplemental measurements and/or evaluations as medically indicated or as requested to elucidate the nature and/or causality of the AE or SAE as fully as possible. This may include additional laboratory tests or investigations, histopathological examinations, or consultation with other health care professionals.
- If a participant dies during participation in the study or during a recognized follow-up period, the investigator will provide a copy of any post-mortem findings including histopathology.
- New or updated information will be recorded in the originally submitted documents.
- The investigator will submit any updated SAE data within 24 hours of receipt of the information.

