8.3. Adverse Events (AEs), Serious Adverse Events (SAEs), and Other Safety Reporting

- The definitions of AEs and SAEs can be found in Section 10.4.
- AEs will be reported by the participant (or, when appropriate, by a caregiver, surrogate, or the participant's legally authorized representative).
- The investigator and any qualified designees are responsible for detecting, documenting, and recording events that meet the definition of an AE or SAE and remain responsible for following up AEs that are serious, considered related to the study intervention or study procedures, or that caused the participant to discontinue the study intervention (see Section 7).
- An unexpected AE is any adverse drug event, which is not listed in the reference safety information in the current IB or is not listed at the specificity or intensity that has been observed in the current study.
- Suspected adverse drug reaction means any AE for which there is a reasonable possibility that the IMP caused the AE.
- Each AE is to be evaluated for duration, severity (using the Common Terminology Criteria for Adverse Events [CTCAE] criteria version 5.0), seriousness, and causal relationship to the IMP or study procedures. The action taken with the investigational drug and the outcome of the event must also be recorded.
- The method of recording, evaluating, and assessing causality of AEs and SAEs and the procedures for completing and transmitting SAE reports are provided in Section 10.4.

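### Protocol 10.4.3 gives two conflicting causality rules for one related/not related rating, so an adverse event with both drug evidence and another explanation fits neither definition

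*Protocol*

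**What the plan says.** The causality part of Section 10.4.3 asks for a binary rating, with no intermediate category, for each occurrence of each AE or SAE. It then gives two sets of instructions.

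- **The test to apply.** "The investigator will use clinical judgment to determine whether there is a reasonable possibility that the IMP caused the AE". The section explains that a reasonable possibility "conveys that there are facts, evidence, and/or arguments to suggest a causal relationship, rather than a relationship cannot be ruled out". Alternative causes are to be considered and investigated. Section 8.3 uses the same standard: "Suspected adverse drug reaction means any AE for which there is a reasonable possibility that the IMP caused the AE".
- **The definitions of the two ratings.** *Related* "means that the AE cannot be explained by the participant's medical condition, other therapies, or an accident", and the timing "is compelling and/or follows a known or suspected response pattern concerning that IMP". *Not related* means that other factors readily explain the event, and it adds: "No plausible temporal or biologic relationship exists between the IMP and the AE".

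The section also says why the rating matters: "The causality assessment is 1 of the criteria used when determining regulatory reporting requirements".

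**The concern.** Showing that nothing else can explain an event is a stricter condition than having evidence that suggests the drug caused it. An event can satisfy the second and fail the first, yet the investigator must choose one of two labels.

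The mixed case is realistic in this trial. Section 8.3.6 makes every infection an adverse event of special interest because the drug lowers IgG. Section 2.3.1 says that the drug may slightly raise infection frequency, with infections of the kind that these patients already get. Section 6.8.2 permits steroids and nonsteroidal immunosuppressants as background treatment. A participant on either has a ready alternative explanation for an infection that the drug may also have caused.

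Three things depend on the label:

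- SUSAR classification (8.3.4, with the link to causality in 10.4.3).
- The investigator's continuing responsibility under 8.3 to follow related AEs, where the event is neither serious, nor of special interest, nor a cause of discontinuation.
- Notification under 8.3.1 of SAEs learned of after participation ends, which is required only if the investigator considers them reasonably related.

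The study is open-label, so raters know the arm. That is a further reason to have one clear rule.

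**Working it through.** No arithmetic applies and the protocol states no figure on this point. The check is logical: cross the presence of a plausible drug link with the presence of an alternative explanation, and apply each rule.

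| Drug link plausible and supported by evidence | Alternative explanation | Reasonable-possibility test (8.3, 10.4.3) | *Related* as defined | *Not related* as defined |
|---|---|---|---|---|
| Yes | No | Related | Met, if the timing is compelling or the response pattern is known or suspected | Not met |
| Yes | Yes | Related | Not met: another cause can explain it | Not met: a plausible relationship exists |
| No | Yes | Not related | Not met | Met, if the other cause readily explains it |
| No | No | Not related | Not met: no compelling timing or response pattern | Not met: nothing else readily explains it |

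The reasonable-possibility test assigns all four rows. The two definitions assign two of the four, and the second row is where they clash with Section 8.3.

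Take an infection during treatment in a participant on a permitted steroid:

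1. *Reasonable possibility.* The IgG-lowering mechanism and the infection risk named in 2.3.1 and 8.3.6 are arguments for a causal link. The test is passed, so under 8.3 this is a suspected adverse drug reaction.
2. *Related.* The response pattern is at least a suspected one, so the second limb can be met. The first limb fails, because another therapy can explain the event.
3. *Not related.* The first limb can be met. The second fails, because a plausible biologic relationship exists.

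The result in step 3 reads the two sentences of *Not related* as both required, which is the natural reading. If either alone were enough, the same event would be *Not related* outright and would contradict 8.3 directly. The text is inconsistent on both readings.

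The thresholds inside the definitions also do not meet. *Related* turns on whether another cause can explain the event, and *Not related* on whether it readily does. *Related* offers compelling timing as one way to meet its second limb, while *Not related* requires that no plausible link exists. Events between these thresholds have no home either.

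**The case against.** The strongest reply is that the decision rule is stated and the definitions only illustrate it. An investigator who finds that an event fits neither definition still has the instruction to judge reasonable possibility, and that instruction rates the mixed event as related. This stands in part. It shows that the text need not mislead, but not that it will not: the definitions follow the instruction in the same list, and nothing says which prevails.

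The protocol also limits the damage, and these points stand in full:

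- All SAEs go to the sponsor within 24 hours whatever their causality (8.3.1), so the sponsor sees every serious event reported during the study.
- All infections are events of special interest whether related or not (8.3.6). Like all SAEs, they are followed to resolution, stabilization or another explanation (8.3.3), unless the participant is lost to follow-up. Infection illustrates the labelling problem well, but follow-up of infections is not at risk.
- The DSMB reviews all available safety data (10.1.5.1), and nothing there filters by relatedness.
- The safety endpoints in Section 3 count AEs and SAEs without regard to relatedness.
- Causality is only one of the criteria for regulatory reporting.

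A reader might infer that the wording systematically pushes infections to *Not related*, or that it would lead to under-reporting of drug-related events and SUSARs. The text does not support either. The *Not related* definition shuts out the mixed event just as the *Related* definition does, so the defect is a gap and not a one-way bias. Mislabelling is possible, not certain.

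**Conclusion.** The contradiction is real and rests on the protocol's own wording. Section 10.4.3 sets two incompatible tests for one forced rating, and an event with both drug evidence and an alternative explanation passes one test while meeting neither definition. Sites could rate such events differently, and some suspected reactions in the sense of 8.3 could be labelled not related.

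The size is modest. What is exposed is the relatedness label and the three things that depend on it: SUSAR classification, follow-up of nonserious related AEs that are not of special interest, and post-study notification of related SAEs. The effect on SUSARs assumes that the investigator's rating carries weight, which 10.4.3 says in general terms only.

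Two of four cells is a count of logical cases, not of events. It may be tempting to conclude that most infections fall in the mixed cell, but the protocol gives no figure for that. Inclusion criterion 7 sets dose conditions for immunosuppressants, steroids and/or acetylcholinesterase inhibitors, so a participant on an acetylcholinesterase inhibitor alone can qualify and has no immunosuppressant to blame. Nor does the text exclude every event that merely has some other possible cause; the wording is that the event cannot be explained otherwise.

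This is an internal contradiction that should be corrected because it concerns safety classification and is cheap to remove. It does not threaten the trial's conclusions.

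**What to change.** Align the two definitions in 10.4.3 with the standard that 8.3 and 10.4.3 already use:

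- *Related*: there is a reasonable possibility that the IMP caused the AE, even if another cause is also possible.
- *Not related*: there is no reasonable possibility that the IMP caused the AE.

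Keep the instruction to consider alternative causes, and say that they are to be weighed and do not by themselves exclude a related rating. Carry the same wording into the eCRF completion guidelines.

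The cost is a change of protocol and guideline wording. No dose, visit, endpoint or sample size changes. The downside is that somewhat more events will be rated related and assessed for expedited reporting, which is what the definition in 8.3 already implies.
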